## 6.1 Study Flow Chart

Procedure/ Assessment	Screening (Day -28 to -1) A	Prime Phase (Weeks 1-7)								Surgery	Boost Phase (Weeks 12- 56)	End of Treatment B	30 Day Follow- Up O	Post- treatment surveil- lance N
		W1 D1	W2 D1	W3 D1	W4 D1	W5 D1	W6 D1	W7 D1	W7 D2					
Visit Windows		+/- 2 days		+/- 5 days		+/- 3 days		+/- 7 days		+/- 7 days		+/- 14 days		
CMP-001 dose number C	N/A	1	2	3	4	5	6	7	N/A	N/A	1-12 (12 doses)			
Nivolumab dose number D	N/A		1		2		3		N/A	N/A	D 1-23 (23 doses – if q2) D 1-12 (12 doses – if q4)			
Tumor Biopsy E	X											X B		
Planned Surgical Evaluation and Resection F	X (evaluation)								X (evaluation)	X (resection)				
Exploratory Biomarker Analyses G		X		X				X			X (every 8 weeks starting with Week 12)			
Informed consent	X													
Eligibility Criteria Assessment	X													
Medical History, Demographics, Cancer History including Prior Cancer Medications	X													
Physical Exam H	X	X	X	X	X	X	X	X		X	X	X	X	
Electrocardiogram (ECG) I	X	X		X				X						
Autoimmune lab panel J	X										X			

HCC 17-169

Clinical laboratory tests (hematology, serum chemistry, other chemistry, urinalysis, coagulation tests and thyroid function) J	X		X		X		X			X		X (CBC, CMP, LDH only)	X (CBC, CMP, LDH only)
Urine Pregnancy Test K	X												
Disease Assessment (CT/MRI) L	X							X		X (every 8 weeks starting with Week 20)			
Stool sampling M	X			X			X			X (every 8 weeks starting with Week 12)			
Dietary history questionnaire N	X			X			X			X (every 8 weeks starting with Week 12)			
Adverse Event Monitoring	Assessed continually from informed consent through EOT + 30 days												
Concomitant Medications	Assessed continually from first CMP-001 dose through EOT + 30 days												
30 Day Follow Up O												X	

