#### **7.1.7.2 Post-treatment surveillance**

Follow up period will start 12 weeks after the last on-treatment time point for patients have completed study treatments or discontinued study therapy for toxicity and have no disease progression. These patients are evaluated per the standard follow-up schedule including imaging (CT vs. CT/PET vs. PET at the discretion of the treating physician) at the intervals directed below. Every 3 months ( $\pm 2$  weeks) if patient is  $< 2$  years from start of follow up period, every 6 months ( $\pm 4$  weeks) if patient is 2-5 years from start of follow up period, and every 12 months ( $\pm 4$  weeks) if patient is  $> 5$  years from start of follow up period for up to 15 years. Patients who develop recurrent melanoma will be followed for information on survival and for information on salvage patterns. The schedule of clinical follow up for these patients will be at the discretion of the treating physicians and according to established Standard of Care. Adverse Events Assessment on the study will continue for all patients until 30 days after the last study drug administration.

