#### **7.1.7.3 Safety follow up visit**

The mandatory Safety Follow-Up Visit should be conducted approximately 30 days after the last dose of trial treatment or before the initiation of a new anti-cancer treatment, whichever comes first. All AEs that occur prior to the Safety Follow-Up Visit should be recorded. Subjects with an AE of Grade  $> 1$  will be followed until the resolution of the AE to Grade 0-1 or until the beginning of a new anti-neoplastic therapy, whichever occurs first. SAEs that occur within 90 days of the end of

treatment or before initiation of a new anti-cancer treatment should also be followed and recorded.

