#### 7.2.3 Timeframe for Adverse Event/Serious Adverse Event Collection

The Investigator is required to record all AEs occurring during the clinical study (21 CFR 312.64[b] and ICH E6 [R1]) starting from the time the subject signs the ICF until 30 days after the last dose of CMP-001 on the AE page of the eCRF. SAEs that occur within 90 days of the end of treatment or before initiation of a new anti-cancer treatment should also be followed and recorded. SAEs as defined in Section 7.2.1.2. must also be reported to the Sponsor or its representative within 24 hours of knowledge of their occurrence, in accordance with Section 7.2.5.

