##### 7.2.3.1 Treatment-related AE

Treatment-related AE/SAE is defined as an AE that started or worsened in severity on or after the date the study drug was first administered. TEAE information will be collected from the time of the subject's first receipt of CMP-001 until 30 days after the last dose of CMP-001.

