##### 7.2.3.2 SAE

SAE information will be collected from the point the subject starts study treatment until 30 days after the last dose of CMP-001. If, at any time after the subject has completed participation in the study, the Investigator or study staff becomes aware of an SAE that they believe is possibly related or related to CMP-001 (see Section 7.2.1.2), then the event and any known details must be reported promptly to the Sponsor or its designee. The reporting instructions described in **Section 7.2.5** must be followed.

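### The end of adverse-event collection is stated inconsistently: 7.2.3 closes it while nivolumab may still be given, and the SAE windows conflict (90 against 30 days)

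*Combined protocol and SAP*

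**What the plan says.** All references are to the combined protocol and SAP.

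General adverse events have four closing rules:

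- **7.2.3 and 7.2.3.1** count from CMP-001 alone. Events are recorded "until 30 days after the last dose of CMP-001 on the AE page of the eCRF", and 7.2.3.1 repeats the anchor: "first receipt of CMP-001 until 30 days after the last dose of CMP-001".
- **7.1.7.2** counts from either drug: "Adverse Events Assessment on the study will continue for all patients until 30 days after the last study drug administration".
- **7.1.7.3** has events recorded up to a safety visit that "should be conducted approximately 30 days after the last dose of trial treatment or before the initiation of a new anti-cancer treatment", taking the earlier of the two.
- **6.1, the flow chart's adverse-event row**: "Assessed continually from informed consent through EOT + 30 days". Note B dates removal from CMP-001 by the investigator's decision to stop it, and allows 7 days for the end-of-treatment assessments. Note O starts the 30-day follow-up from completion of Boost cycle 12.

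Serious events have two windows. Section 7.2.3 covers "SAEs that occur within 90 days of the end of treatment or before initiation of a new anti-cancer treatment", and 7.1.7.3 agrees. Section 7.2.3.2 says: "SAE information will be collected from the point the subject starts study treatment until 30 days after the last dose of CMP-001". Section 7.1.3.1 mentions only related SAEs for the 90 days, but defers to 7.2 for detail.

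Sections 5.2.2.4 and 5.7 allow a patient to stay on nivolumab after CMP-001 is stopped. Section 8.1 plans surgery at weeks 8-10, and Boost starts at week 12. None of the closing rules mentions surgery.

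**The concern.** Safety is a secondary objective (3.2), and the safety tables in 8.5 can hold only what was recorded. If the governing section ends recording 30 days after CMP-001 while nivolumab continues, nivolumab-related events that begin later fall outside the window that 7.2.3 sets. With two SAE windows in neighbouring paragraphs, it is unclear whether an unrelated SAE in the second or third month counts. Two patients with the same course could therefore have different recording periods, depending on which section staff follow and, under the flow chart, on when the decision to stop CMP-001 is dated. A smaller gap arises because nothing ties collection to the planned operation.

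**Working it through.** The plan states no closing day, so there is no figure to reproduce. The check is calendar arithmetic on the nominal schedule.

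**Inputs.** W1D1 = day 1, and week *w* day 1 = 1 + 7(*w* - 1).

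- Last Prime CMP-001 dose, W7D1: 1 + 7×6 = day 43.
- Last Prime nivolumab dose, W6D1: 1 + 7×5 = day 36.
- First Boost visit, W12D1: 1 + 7×11 = day 78.
- Last Boost nivolumab dose, W56D1: 1 + 7×55 = day 386.
- Surgery at weeks 8-10 (8.1): days 50 to 70.

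**Step 1. CMP-001 stops after W7D1 and nivolumab continues alone to week 56.**

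| Rule | Arithmetic | Closes on day |
|---|---|---|
| 7.2.3, 7.2.3.1 | 43 + 30 | 73 |
| 7.1.7.2 | 386 + 30 | 416 |
| 7.1.7.3 | about 386 + 30, or earlier at new therapy | about 416 |
| Flow chart, stop decided at W7D1 | 43 + (0 to 7) + 30 | 73-80 |
| Flow chart, stop decided at W12D1 | 78 + (0 to 7) + 30 | 108-115 |

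Sections 7.2.3 and 7.1.7.2 differ by 416 - 73 = 343 days. Day 73 falls 78 - 73 = 5 days before the first Boost nivolumab dose. The flow chart, anchored by note B on CMP-001, also closes during nivolumab treatment.

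The gap shrinks with a later stop. If the last CMP-001 dose is Boost dose 10 (week 12 + 4×9 = 48, day 330), 7.2.3 closes on day 360, still before the last nivolumab dose on day 386. If it is dose 11 (week 52, day 358), 7.2.3 closes on day 388, after the last nivolumab dose. So 7.2.3 ends recording during treatment whenever nivolumab runs more than 30 days past the last CMP-001 dose.

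**Step 2. SAEs, last dose at W7D1, end of treatment taken as the last dose.** Section 7.2.3 gives 43 + 90 = day 133. Section 7.2.3.2 gives 43 + 30 = day 73. They disagree for 133 - 73 = 60 days.

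**Step 3. Prime completed, no Boost dose.** CMP-001 is the later drug (day 43 against day 36), so both last-dose rules close on day 73. Post-operative days covered = 73 - surgery day:

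- Surgery on day 50: 23 days.
- Surgery on day 70: 3 days.

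The one-week rescheduling window in section 6 moves closure to days 66-80. Under the flow chart, a stop decided on the day of surgery gives 30 to 37 post-operative days. Note O does not help, because this patient never reaches Boost cycle 12.

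**Step 4. CMP-001 resumed in Boost.** The post-operative period is covered under every rule. If both drugs end at week 56, the last-dose rules all give day 416.

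**The case against.** The strongest reply is that a team obeying every section at once would simply use the latest date. Section 7.1.7.2 applies to all patients, two sections agree on 90 days for SAEs, and this is a single-center study. In addition, 7.2.3.2 still requires a report if staff "becomes aware of an SAE that they believe is possibly related or related to CMP-001", and 7.2.7 has similar wording. This stands as a reason to expect limited loss in practice, and it narrows the SAE uncertainty to unrelated events. It does not settle the rule. Nowhere does the protocol say that the latest date governs, and 7.2.3 is the section headed as the collection timeframe.

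A reader might infer something stronger: that post-operative complications go unrecorded, or that collection closes before surgery. The documents do not support that.

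- Closure before surgery appears only if the 2 to 4 weeks in 5.2 are counted from the end of week 7 (49 + 28 = day 77, 4 days after day 73). Under 8.1, surgery always precedes closure.
- W7D1 is known to be the last dose only once Boost is abandoned. Until then the patient is on study, with continual assessment and an examination at surgery, so earlier post-operative events would ordinarily be recorded. The gap matters mainly when stopping is decided before or soon after surgery.
- Section 7.2.5.2 separately requires cutaneous injection-site events to be reported, whether or not related, for 90 days after treatment (30 with new therapy). Some wound events would be caught there.
- Events that begin inside the window are followed under 7.2.7.
- Section 8.5 defines toxicity as events at least possibly related to treatment, so ordinary surgical complications judged unrelated would not enter its tables.
- The documents set no 30-day post-operative standard. That benchmark is mine.

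**Conclusion.** The collection rules are wrong as written because they conflict. The main defect is that 7.2.3 and 7.2.3.1 anchor on CMP-001 although nivolumab may continue alone. For CMP-001 stopped at W7D1 and nivolumab given to week 56, the gap is 343 days against 7.1.7.2. The SAE windows differ by 60 days for a last dose at W7D1, and that uncertainty concerns unrelated SAEs. The lack of any link to surgery is secondary. It concerns non-serious events in patients with no Boost dose that are not already captured as Events of Clinical Interest.

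These figures assume the nominal calendar. A CMP-001 stop earlier in Prime would widen the first gap. The documents do not say how many patients will stop CMP-001 or miss Boost. Each is 1/33 = 3.0% of the planned sample, the number may be small, and the effect on the safety estimates cannot be computed. Severity is minor.

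**What to change.** (a) Put one rule in 7.2.3, 7.2.3.1, 7.1.7.2, 7.1.7.3, the flow-chart row and note O. All adverse events are recorded until 30 days after the last dose of either study drug. For patients who have surgery and receive no Boost dose, recording runs to 30 days after the last definitive surgical procedure if that is later. The new-therapy cut-off in 7.1.7.3 should not be carried into the other sections, and it should not end the post-operative window.

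(b) Align 7.2.3.2 and 7.1.3.1 to the 90-day window for all SAEs, counted from the last dose of either drug.

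Cost: protocol wording, with no new procedure. For a no-Boost patient with surgery at weeks 8-10, recording would run to days 80-100 instead of day 73, which is 7 to 27 extra days by chart review or telephone. For nivolumab-alone patients, the rule asks for no more than 7.1.7.2 already does. Reported event counts may rise slightly.

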##### 7.2.3.1 Treatment-related AE

Treatment-related AE/SAE is defined as an AE that started or worsened in severity on or after the date the study drug was first administered. TEAE information will be collected from the time of the subject's first receipt of CMP-001 until 30 days after the last dose of CMP-001.

##### 7.2.3.2 SAE

SAE information will be collected from the point the subject starts study treatment until 30 days after the last dose of CMP-001. If, at any time after the subject has completed participation in the study, the Investigator or study staff becomes aware of an SAE that they believe is possibly related or related to CMP-001 (see Section 7.2.1.2), then the event and any known details must be reported promptly to the Sponsor or its designee. The reporting instructions described in **Section 7.2.5** must be followed.

#### 7.2.4 Recording Adverse Events/Serious Adverse Events

All AEs and SAEs experienced by a subject will be recorded on the appropriate eCRF. Information including a concise description of the event; date and time of event onset and resolution; determination of seriousness, severity, corrective treatment, outcome, relationship to study drug; and action taken regarding the study drug will be recorded. Vital signs, laboratory results, and other safety

assessments noted in **Section 7.1.2** will be recorded as AEs if they are determined to be clinically significant findings in the opinion of the Investigator. When possible, a diagnosis should be recorded as an AE, rather than symptoms or isolated laboratory abnormalities related to that diagnosis. However, when flu-like or cytokine release-like symptoms are reported, each individual symptom should be recorded as a separate AE in the Electronic Data Capture (EDC) system. A medical or surgical procedure is not an AE; rather the condition leading to the procedure should be recorded as the AE. If the condition is not known, the procedure must be recorded as an AE instead. Similarly, death is not an AE, but is rather the outcome of the AE(s) that resulted in death. If the AE(s) leading to death are not known, then death must be reported as an AE.

All SAEs experienced by the subject will be entered into the CTMA and reported to the Sponsor or designee, in accordance with Section **7.2.5.1**.

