### **7.2 Adverse and Serious Adverse Events**

#### **7.2.1 Definitions**

##### **7.2.1.1 Adverse events (AE)**

An AE is an untoward or medical occurrence associated with the use of study drug (active or placebo drug, biologic, or device) in clinical investigation subjects, which does not necessarily have a causal relationship with the study drug. An AE can therefore be any unfavorable and unintended symptom, sign, disease or condition, or test abnormality whether or not considered related to study drug. AEs that do not meet the definition for an SAE are considered non-serious AEs.

AEs include:

- Changes described by the subject or signs observed by the Investigator or medical staff.
- Test abnormalities (i.e., laboratory tests, ECGs) that result in an alteration in medical care (diagnostic or therapeutic).

Disease Progression is **not** considered an AE in this study.

Abnormalities present at baseline are considered AEs only if they reoccur after resolution or they worsen during the study.

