### 8.2 Safety Monitoring

The PD-1/CMP-001 combination has been tested in the PD-1 refractory setting in melanoma including in a phase I study that evaluated multiple doses of CMP-001 including 5mg, 7.5mg and 10mg. The safety profile observed thus far suggests that the **risk of additive toxicities are unlikely to be significantly increased** in the neoadjuvant setting. Further, the dose being tested in this study (5mg) is 50% the ceiling dose tested in other CMP-001 studies in combination with PD-1 inhibitors, none of which reported a toxicity rate >33%.

However, in the context of this neoadjuvant trial, we will monitor dose limiting toxicities (DLTs) for 4 weeks for the 1st 3 patients accrued. DLT is defined as any adverse event(s) (AEs) considered possibly, probably, or definitely related to the CMP-001 plus nivolumab regimen, which occur during the first 15 days of therapy (i.e. following 3 doses of CMP-001; W1D1, W2D1, W3D1) IN the Prime phase only. Attribution of AEs specifically to either CMP-001 or nivolumab is challenging, therefore, the relationship to CMP-001 should be based on attribution to the combination of the two drugs. During DLT monitoring period, no further accrual will be permitted. Any patient who has started the studied treatment will be evaluable for safety.

The following AEs will be considered DLTs if deemed related to study therapy:

- Hematologic
  - Grade 4 neutropenia
  - Febrile neutropenia, defined as absolute neutrophil count (ANC)  $\leq 1000/\text{mm}^3$  with a temperature of  $\geq 38.3$  degrees °C
  - Grade  $\geq 3$  neutropenic infection
  - Grade  $\geq 3$  thrombocytopenia with bleeding
  - Grade 4 thrombocytopenia
- Non-hematologic
  - Grade  $\geq 3$  toxicities (non-laboratory)
  - Grade  $\geq 3$  nausea, vomiting or diarrhea despite maximal medical intervention
  - Grade 4 aspartate aminotransferase (AST) and alanine aminotransferase (ALT)

- Other (non AST/ALT) non-hematologic Grade  $\geq 3$  laboratory value if the abnormality leads to overnight hospitalization

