### **8.5 Safety Analysis**

As per NCI CTCAE Version 4.0, the term toxicity is defined as adverse events that are classified as either possibly, probably, or definitely related to study treatment. The maximum grade for each type of toxicity will be recorded for each patient, and frequency tables will be reviewed to determine toxicity patterns.

As CMP-001 has previously been dose-escalated in combination with PD-1 inhibitors pembrolizumab and nivolumab with minimal additional toxicities, no “dose-escalation” will be performed in this study. However, to accurately capture toxicities for this novel combination, we will be monitoring toxicities closely. The detailed data and safety monitoring plan is in **Section 8.7**.

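### Sections 7.2.1.1 and 7.2.4 set different rules for when a laboratory abnormality is an adverse event, and Section 8.5 has no laboratory-based summary to show what the investigator's judgment leaves out

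*Combined protocol and SAP*

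**What the plan says.** **Recording.** Section 7.2.4 (Recording Adverse Events/Serious Adverse Events) says that vital signs, laboratory results and other safety assessments "will be recorded as AEs if they are determined to be clinically significant findings in the opinion of the Investigator". It places those assessments in Section 7.1.2.

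**Definition.** Section 7.2.1.1 is wider. Under its general definition an adverse event can be an unfavorable and unintended symptom, sign, "disease or condition, or test abnormality whether or not considered related to study drug". A list of what adverse events include then names "Test abnormalities (i.e., laboratory tests, ECGs) that result in an alteration in medical care (diagnostic or therapeutic").

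**Analysis.** In Section 8.5, "the term toxicity is defined as adverse events that are classified as either possibly, probably, or definitely related to study treatment", and "The maximum grade for each type of toxicity will be recorded for each patient". Frequency tables follow. Section 7.2.2.2 has the investigator rate causality for each adverse event.

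**Dose-limiting toxicity.** Section 8.2 states that "DLT is defined as any adverse event(s) (AEs) considered possibly, probably, or definitely related to the CMP-001 plus nivolumab regimen", within the first 15 days of therapy. Its list sets some laboratory events by grade alone, for example "Grade 4 neutropenia". Other non-hematologic laboratory values of Grade 3 or higher count if they lead to an overnight hospital stay.

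**Holds.** The text of Sections 5.2.1.2 and 5.2.2.4 withholds drug for related hematologic toxicity at Grade 4 and for non-hematologic toxicity from Grade 3, laboratory abnormalities included.

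**The concern.** Safety is a secondary objective (Section 3.2), and Section 8.5 is its planned analysis. The trial has one arm and no blinding, so the person who decides whether a laboratory value matters knows the treatment.

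Under Section 7.2.4 that decision comes before the value is recorded, graded and rated for causality. A value that is not declared an adverse event gets no causality rating and cannot enter the maximum-grade table. Nothing else in the plan tabulates laboratory grades, so the final report would not reveal the omission.

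Two investigators who follow different sections could also record the same value differently: one under the general definition in 7.2.1.1, the other under clinical significance in 7.2.4. The laboratory toxicity rates would then depend partly on which section was followed.

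**Working it through.** The plan gives no figure to reproduce on this point, so the check sets the sections side by side and asks which laboratory abnormalities reach the Section 8.5 table.

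**Step 1. Which values are brought in whatever the investigator thinks of clinical significance?** A value that changes care is an adverse event under 7.2.1.1.

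| Laboratory event | What the plan requires | Captured through 7.2.1.1? |
|---|---|---|
| Grade 4 neutropenia, Grade 4 thrombocytopenia, Grade 4 AST and ALT in the DLT window | DLT by grade (8.2); both drugs withheld | Yes |
| Other non-hematologic Grade 3 or higher value in the DLT window | DLT if it leads to overnight hospitalization (8.2) | Yes, where the DLT line is met |
| Related Grade 4 hematologic value, any time | Hold (5.2.1.2, 5.2.2.4) | Yes |
| Related non-hematologic value of Grade 3 or higher, any time | Hold (5.2.1.2, 5.2.2.4) | Yes |
| AST, ALT or bilirubin from Grade 2 | Hold or discontinuation (Table 5.2.1.2-1) | Yes |
| Grade 3 hematologic value without a complication | No hold in the text of 5.2.1.2 and 5.2.2.4; the catch-all row of Table 5.2.1.2-1 lists Grade 3 | Unclear |
| Lower-grade values that change nothing in care | No action required | Only by the general definition, or if judged clinically significant |

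**Step 2. What is left exposed?** The last two rows. A smaller remainder cuts across the table: the hold rules apply to drug-related toxicity, so a value dismissed before relatedness is considered could still be omitted.

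**Step 3. Is the Grade 3 hematologic row a real class of event?** Table 4.1.4-1 reports related anemia in 4 of 28 Schedule A subjects (4/28 = 14.3%) in the CMP-001 and pembrolizumab study. No grade is given, so this shows only that a related hematologic abnormality is plausible. It does not give the rate of Grade 3 values.

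**Step 4. Can the loss be sized?** Not from the documents, which give neither the true rate of such values nor the share that would be declared. For illustration, with 33 patients (Section 8.3):

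expected patients in the table = 33 × true rate of exposed toxicity × share declared.

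| Assumed true rate | All declared | 75% declared | 50% declared |
|---|---|---|---|
| 5% | 33 × 0.05 = 1.65 | 1.24 | 0.83 |
| 10% | 33 × 0.10 = 3.30 | 2.48 | 1.65 |
| 20% | 33 × 0.20 = 6.60 | 4.95 | 3.30 |

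Both inputs are assumptions. One patient is 1/33 = 3.0 percentage points, so even a small loss shows in the reported rate.

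**Step 5. Is the information there to do better?** The study flow chart schedules clinical laboratory tests at screening and during treatment, and Section 7.1.5.1 requires results to be reviewed before each dose. The tests are therefore already being done. No section says that the results are graded independently of the adverse-event page.

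**The case against.** The strongest reply is that the plan already captures what matters. Section 7.2.4 opens by requiring all adverse events to be recorded, and its sentence on clinical significance does not say that this is the only route. The general definition in 7.2.1.1 admits any unfavorable test abnormality. The hold rules reach most serious laboratory toxicity, and Section 5.2.1.2 itself speaks of a laboratory adverse event still at Grade 2. Patients are reviewed weekly under Section 8.7. No decision rule uses the Section 8.5 table, because the go/no-go rule rests on major pathologic response alone.

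Much of this stands. A reader might infer that a laboratory value becomes an adverse event only if it is judged significant or changes care. The general definition contradicts that.

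A reader might also infer that the DLT count is exposed. It is not in any practical sense: laboratory DLTs are set by grade or by hospitalization, and they force withholding or admission, which makes them adverse events under 7.2.1.1. The remaining discretion is attribution to study therapy, which Section 8.2 states openly. There is some circularity, since a DLT is defined as a related adverse event, but one clarifying sentence removes it.

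The reply does not remove the mismatch between 7.2.1.1 and 7.2.4, and it does not supply a laboratory-based summary. It also relies on the Grade 3 catch-all row of Table 5.2.1.2-1 to cover Grade 3 hematologic values, and that row conflicts with the section's own text.

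**Conclusion.** The point holds in a limited form. The two sections give different recording rules, one of them rests on the investigator's opinion, and Section 8.5 draws only on what was recorded and judged related. Laboratory toxicity judged not clinically significant can be missing from the safety results, and any error lowers the reported rates.

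The exposure is mainly lower-grade values and Grade 3 hematologic values without a hold. The documents do not support extending it to Grade 3-4 laboratory toxicity in general, because related Grade 4 hematologic and Grade 3 or higher non-hematologic values mostly return through the hold rules.

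The size is unknown. The figures in the working show only what assumed rates would imply. The consequence is for the descriptive safety report; sample size, error rates and the efficacy decision are untouched. The change is worth making because it is cheap and removes the opinion filter.

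**What to change.** 1. **Section 8.5.** Add a table of worst on-treatment CTCAE grade and shift from baseline for each laboratory parameter that CTCAE grades. Compute it from the scheduled laboratory results, whether or not they were declared adverse events. This is the main change.
2. **Sections 7.2.4 and 7.2.1.1.** Align them so that one recording rule applies. State that any value meeting a laboratory DLT line in Section 8.2 is recorded as an adverse event and given a causality rating.
3. **Section 5.2.1.2.** Reconcile the text, which starts the hematologic hold at Grade 4, with the catch-all row for other drug-related toxicity in Table 5.2.1.2-1, which lists Grade 3. Which threshold applies is for the trial's clinicians to settle.
4. **Editorial.** Section 7.2.4 cites 7.1.2, which is now Administrative Procedures. The table of contents lists that number as clinical procedures, so this looks like a renumbering slip. The reference should be to 7.1.3 for vital signs and 7.1.5 for laboratory tests.

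**Cost.** Wording changes and one extra table. There is some added data entry if laboratory values are not already held in analyzable form, which the documents do not say. Reported laboratory toxicity may be slightly higher. No new test or visit is needed.
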